#### 4.5.8. Injection Site Evaluations

Injection site evaluations will be performed according to the SoA (Table 1-1) and will be summarized for pivotal and all patients for all visits by treatment received according to severity (none, mild, moderate, severe) and type of reaction (erythema, edema, induration, itching, pain or tenderness, or other reaction), as needed. For patients reporting more than one occurrence of the same type of reaction, the most severe reaction will be used for the summary.

A by-patient listing will be provided for all injection site evaluations and will also include measurement (if applicable).

#### 4.5.9. Laboratory Data

Clinical laboratory values will be expressed in the International System of Units (SI).

The actual value, change from baseline, and percent from baseline to each on-study evaluation will be summarized for each clinical laboratory parameter by visit and treatment received for pivotal and all patients, as needed. Clinical laboratory parameters include:

##### *Hematology*

Hematocrit, Hemoglobin, CCI, Mean Corpuscular Hemoglobin, Erythrocytes, Mean Corpuscular Volume, Platelets, Leukocytes, Differentials (absolute and percent; Basophils, Eosinophils, Neutrophils, Lymphocytes, Monocytes).

##### *Chemistry*

Glucose, Blood urea nitrogen, Uric acid, Creatinine, Creatine phosphokinase, Sodium, Potassium, Chloride, Bicarbonate, Calcium, Lactate dehydrogenase, Magnesium, Phosphate, Total bilirubin, Direct bilirubin, Alkaline phosphatase, Alanine transaminase, Aspartate transaminase, Albumin, Gamma-glutamyl transferase, Total protein.

##### *Urinalysis*

Color, clarity, leukocyte esterase, nitrite, urobilinogen, urine protein, pH, specific gravity, Urine ketones, Urine bilirubin, Urine glucose, Blood.

In the event of repeat values, the last non-missing value per study day/time will be used.

Abnormal evaluations will be summarized in a table by treatment received for pivotal and all patients, as needed.

Shift tables of change in abnormal status (low/normal/high) of laboratory parameters from baseline to every planned post-baseline visit will be presented for hematology and clinical chemistry by treatment received for pivotal and all patients, as needed.

All laboratory data, including pregnancy test results and FSH, will be provided in data listings.

#### 4.5.10. 12-Lead Electrocardiogram

ECG results will be measured as shown in the SoA (Table 1-1).

All ECG data, including overall interpretation, will be provided in a by-patient data listing.

#### 4.5.11. Vital Signs

Vital signs will be measured as according to the SoA (Table 1-1). Aside from those used in efficacy evaluations, the actual value, change from baseline, and percent change from baseline

of temperature, HR, systolic Blood Pressure (BP), diastolic BP, and respiratory rate will be summarized descriptively by visit and treatment received for pivotal and all patients, as needed.

A by-patient listing of all vital signs will be provided.

#### **4.5.12. Physical Examination and Comprehensive Skin Examination**

Physical and comprehensive skin examinations will be performed according to the SOA (Table 1-1). Results of the physical examinations will be provided in a shift table, summarizing the shift from baseline to each visit for pivotal and all patients by treatment received, as needed. Skin examination findings will be presented in a shift table, summarizing the shift from baseline to each visit for a given region by treatment received for pivotal and all patients, as needed.

A separate, by-visit descriptive summary of tanner staging assessment will be provided by treatment received for pivotal and all patients, as applicable.

Separate by-patient listings of all physical examination, tanner staging, and skin examination findings will be provided.

#### **4.5.13. Concomitant Medications**

A prior medication is defined as any medication that was started before the time of first dose date.

Concomitant medications are defined as medications either ongoing at the time of first dose date or which start on or after the first dose date but before drug discontinuation. A medication may be considered both prior and concomitant.

Concomitant medications will be assessed according to the schedule in [Table 1-1](#) and coded using the WHO Drug Dictionary, version March 1, 2021, or later. The use of prior and concomitant medications will be included in separate summary tables by treatment received for pivotal and all patients, as needed. Prior and concomitant medications will be tabulated by Anatomical Therapeutic Chemical class and Preferred Term.

Prior and concomitant medications will also be included in a by-patient data listing.

#### **4.5.14. Anti-RM-493 Antibody Measurements**

Blood samples for Anti-RM-493 antibody assessment will be collected as shown in the SoA (Table 1-1).

Results will be provided in a by-patient listing, including the date of the assessment and result.

#### **4.5.15. Ambulatory BP Monitoring (ABPM)**

At select sites in North America and Europe, ABPM will be conducted outside of the clinic setting in all patients  $\geq 4$  years of age. For patients  $\leq 12$  years of age, both caregiver and Investigator will confirm feasibility of patient compliance in this assessment. The ABPM monitor will measure BP (systolic and diastolic), pulse pressure (mmHg), mean arterial blood pressure (mmHg) and HR in 30-minute intervals for each 24-hour period. ABPM assessments

will require patients to wear the monitor at each time point for any 24-hour period before Day 1 (conducted during Screening), Week 24, and EOT Visit (occurs after 52 weeks on a therapeutic dose), per SoA (Table 1-1).

Assuming sufficient patients, ABPM parameters will be summarized by visit, timepoint (Nighttime, daytime, 24 hours overall), and treatment received. Nighttime results will be defined to include all reported measurements between 8:00PM (20:00 hours) to 5:59AM (05:59 hours) the next day. Daytime results will be defined to include all reported measurements between 6:00AM (06:00 hours) to 7:59PM (19:59 hours).

Nighttime, daytime, and 24 hour overall values will be derived using the following steps:

For derivation purposes, the reported collection time, in 24hour time system, will be mapped as  $\text{Hour} = \text{Floor}(\text{Time})$ . For example, times from 07:00-07:59 will be mapped to  $\text{Hour}=07:00$ . The hourly value will be equal to the average of non-missing values mapped to that specific hour. For example, since ABPM measurements are in 30-minute intervals, the 7:00 value may be defined as the average of the 7:00 and 7:30 collected values, as applicable.

Once all hourly values are generated, the timepoint (nighttime, daytime, 24 hour overall) values will be derived as the average of all non-missing hourly values according to the timepoint definitions above.

Change from baseline in nighttime, daytime, and 24 hour overall values will be derived using the following steps:

As noted above, hourly values will be generated for each of the 24 hours of ABPM monitoring. For post-baseline visits, each hourly value will first have its own change from baseline based upon the baseline value for the same hour. For example, change from baseline at 7:00 will be calculated as post-baseline 7:00 value minus baseline 7:00 value.

Once all hourly change from baselines are derived, the timepoint (nighttime, daytime, 24 hour overall) change from baseline values will be derived as the average of all non-missing hourly change from baseline values according to the timepoint definitions above.

The actual observed and change from baseline in ABPM parameters will be summarized by timepoint, visit, and treatment received for pivotal and all patients, as needed.

A by-patient listing for all ABPM parameters will be provided.

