**Table 3: Objectives and Endpoints**

Objective	Endpoint
Safety	
To evaluate the safety and tolerability of setmelanotide compared to placebo	– Safety and tolerability assessed by the frequency and severity of adverse events (AEs), AEs of special interest (AESIs), vital signs, and laboratory evaluations from Baseline after approximately 52 weeks on a therapeutic regimen of setmelanotide compared to placebo
To evaluate the effect of setmelanotide on blood pressure (BP)	– Change in ambulatory BP and heart rate (HR) from Baseline after approximately 52 weeks on a therapeutic regimen of setmelanotide compared to placebo (in patients $\geq 12$ years)

CCI

CCI

CCI

CCI

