**CCI**  

#### **4.3. Treatment Discontinuation and Withdrawal from Trial**

Given this rare patient population, every effort should be made to encourage and keep patients enrolled in the trial until completion, unless there are any safety concerns necessitating withdrawal of the trial treatment or the patient from the trial. If patients must discontinue

treatment, they should be encouraged to continue to participate in all regular trial visits and assessments (other than dosing and pharmacokinetic [PK] assessments), if possible, as a Retained Dropout.

The Sponsor will provide assistance for patient and caregiver travel and will provide other necessary logistical support to ease the burden on the patient in order to facilitate compliance and completion of trial participation.

Discontinuation of trial treatment or skipped visits/doses may be allowed without withdrawal from the trial upon consultation with the Sponsor and CRO Medical Monitor.

Patients who either discontinue treatment or withdraw from the trial before completing the trial are to attend an Early Termination of Treatment (ETT) Visit as soon as possible after the last dose of trial treatment. Patients who prematurely discontinue treatment may also be required to complete the Safety Follow-up Visit (SFV), if applicable (Section 5.1.4).

If the ETT Visit occurs 4 weeks or later following the last dose of trial treatment, then the ETT Visit will replace the SFV if no ongoing AEs are being monitored. Patients who prematurely discontinue study drug treatment will continue to complete all scheduled study visits for assessments following completion of the ETT.

Patients who complete the trial will have the opportunity to participate in the LTE with open-label setmelanotide (or Bridging visits if the LTE is not yet available). Patients must meet the LTE eligibility criteria and should discuss eligibility with the Investigator.

Patients who discontinue trial treatment but remain in the trial should be encouraged to attend all planned visits until the final Visit. See Section 5.1.3. Patients who discontinue treatment will be counted as non-responders, irrespective of treatment assignment. Patients who discontinue treatment prematurely are not eligible to enroll in the optional LTE. Exceptions may be made in consultation with the Sponsor.

Patients who withdraw from the trial will attend an ETT visit only.

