**1.4.3. Safety Parameters**

The safety endpoints are:

PPD

- Safety and tolerability assessed by the frequency and severity of AEs, AEs of special interest, vital signs, and laboratory evaluations from Baseline after approximately 52 weeks on a therapeutic regimen of setmelanotide compared to placebo
- Change in ambulatory BP and heart rate (HR) from Baseline after approximately 52 weeks on a therapeutic regimen of setmelanotide compared to placebo (in patients  $\geq 12$  years)

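### The ambulatory BP and heart rate endpoint is defined against placebo in patients aged 12 and over, but SAP 4.5.15 pools ages 4 and up and gives no between-arm estimate

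*SAP*

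**What the plan says.** **Definition.** SAP 1.4.3 gives the endpoint as "Change in ambulatory BP and heart rate (HR) from Baseline after approximately 52 weeks on a therapeutic regimen of setmelanotide compared to placebo", followed by a limit to patients aged 12 and over. Protocol Table 3 has the same limit: "setmelanotide compared to placebo (in patients $\geq 12$ years". The safety rows of the protocol synopsis (Section 1.1) give the endpoint without any age limit.

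**Measurement.** Protocol 6.8.2 and SAP 4.5.15 collect ABPM at select sites in North America and Europe from age 4: "ABPM will be conducted outside of the clinic setting in all patients" of that age and above. Recordings are scheduled before Day 1, Week 24 and EOT. None is scheduled at the early termination visit.

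**Analysis.** SAP 4.5.15 plans the following: "Assuming sufficient patients, ABPM parameters will be summarized by visit, timepoint (Nighttime, daytime, 24 hours overall), and treatment received". It ends with: "The actual observed and change from baseline in ABPM parameters will be summarized by timepoint, visit, and treatment received for pivotal and all patients". No age cut, arm difference, interval or on-drug condition appears. The summaries depend on there being enough patients, and no number is stated. SAP 4.5 uses the Safety Set, which SAP 2.1 defines as everyone with at least one dose, by treatment received.

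**Patients who stop drug.** Protocol 4.3 says of them: "they should be encouraged to continue to participate in all regular trial visits and assessments (other than dosing and pharmacokinetic [PK] assessments". ABPM is not among the exceptions, and SAP 1.3.1 likewise has retained dropouts complete all assessments.

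**The concern.** BP is a safety objective of its own in Protocol Table 3. Protocol 2.3 names hypertension as a potential mechanism-based event, while reporting that it has not been observed in the programme. ABPM is the only planned measure covering 24 hours. Scheduled clinic readings fall before the day's dose, because Protocol Section 6 puts vital signs before blood draws and footnote 27 of the Schedule of Assessments puts in-clinic dosing after the draws.

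The ABPM analysis should therefore return the quantity the endpoint names. As written it returns by-arm means over a wider age range and leaves the reader to form the comparison. For the defined population even that is not possible from the planned tables, because ages 4 to 11 are not separated out. The plan is also silent on recordings made after a patient has stopped drug. For a safety measure, any attenuation from these would be in the unsafe direction.

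**Working it through.** **1. Definition against analysis**

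| Element | Protocol Table 3, SAP 1.4.3 | SAP 4.5.15 |
|---|---|---|
| Age | 12 and over (no limit in the synopsis) | 4 and over, no split |
| Contrast | Change, against placebo | Summaries by treatment received |
| Drug condition | About 52 weeks on a therapeutic regimen | None stated |

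**2. Whether another section fills the gap**
- SAP 3.8 lists an age bracket split, but the analyses are optional and are described for efficacy endpoints.
- SAP 4.3.6.11 fits an ANCOVA to blood pressure as a cardiometabolic parameter, in the mITT, adjusted for all three age groups. It does not name ABPM. If ABPM were meant, ages would still be pooled.
- SAP 4.5.11 summarises clinic vital signs descriptively.

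None of these yields the ABPM contrast in patients aged 12 and over.

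**3. The plan's own figure, to fix what its 20% means**

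The documents give no sample size, SD, effect or power for ABPM. The stated power of about 99.5% concerns BMI. With 20% dropout, 80 and 40 become 64 and 32:
- SE = 10 × √(1/64 + 1/32) = 2.165
- 10/2.165 = 4.619; 4.619 − 1.96 = 2.659; power = 0.9961 (0.9955 by noncentral t)

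The figure reproduces. The 20% there stands for patients who contribute no outcome, so it is not a planned share of off-drug recordings. It is used below only as the top of an assumed range.

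**4. Off-drug recordings**

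If a share f of setmelanotide recordings is off drug and the effect fully reverses, the observed effect is D × (1 − f).

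| True rise D (mmHg) | f = 5% | f = 10% | f = 20% |
|---|---|---|---|
| 3 | 2.85 | 2.7 | 2.4 |
| 5 | 4.75 | 4.5 | 4.0 |

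**5. Age pooling**

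If a share w is under 12 and their effect is r times that at 12 and over, the pooled effect is D × [(1 − w) + r × w]. For D = 5 and an assumed w = 30%:
- r = 0 gives 3.5
- r = 0.5 gives 4.25
- r = 1 gives 5.0
- r = 1.5 gives 5.75

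The direction depends on r, which the documents do not give.

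**6. Width of the missing interval**

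Half-width = 1.96 × SD × √(1/n₁ + 1/n₂). With an assumed 40 against 20, this is 0.537 × SD: 4.3, 5.4 and 6.4 mmHg at SD 8, 10 and 12 (4.4, 5.5 and 6.6 with the t quantile). With the t quantile, 64 against 32 gives 3.4 to 5.2, and 20 against 10 gives 6.3 to 9.5.

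**The case against.** **Comparison wording.** SAP 1.4.3 uses the same comparison phrase for adverse events, vital signs and laboratory values, and Protocol 7.6 plans descriptive safety summaries, so the phrase does not promise a test. By-arm n, mean and SD would also let a reader form an unadjusted difference. Both points stand, and they argue for a descriptive difference without a test. They do not supply the contrast for patients aged 12 and over.

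**Redaction.** ABPM text is blacked out in Protocol 6.8.2 and footnote 31, and SAP Section 5 on changed analyses is redacted. An explanation of the age range or a recording-validity rule could sit there. For that reason no claim is made here about minimum recording hours. The visible mismatch still needs reconciling.

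**Diluted signal.** A reader might infer that the plan as a whole dilutes a BP rise. The documents do not support that:
- Pooling ages has no known direction.
- A missing interval changes no mean.
- Use of off-drug recordings is inferred from Protocol 4.3, SAP 1.3.1 and SAP 2.1, not stated. The inference is clearest at Week 24, because the EOT recording is described as following 52 weeks on a therapeutic dose. Attenuation also requires reversal off drug.

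**Missing night hours.** A reader might also infer that losing the night inflates the 24-hour result, since "values will be derived as the average of all non-missing hourly values according to the timepoint definitions above". That rule governs actual values. SAP 4.5.15 computes change hour against the same baseline hour before averaging, so a day-night imbalance in level does not enter the change. Only coverage is affected.

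**On-drug analysis.** Making an on-drug table the main one would select on a post-randomisation event. If patients stop because BP rose, it removes them, which is also the unsafe direction. This objection stands and shapes the fix.

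**Conclusion.** The point holds in a limited form. The endpoint definition and the ABPM analysis disagree on age, the synopsis disagrees with Table 3, and no section estimates the comparison with placebo for ABPM. These rest on the visible text and need no assumption.

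The off-drug issue is secondary. Attenuation is bounded by the off-drug share: 0.25 to 1.0 mmHg of a true 5 mmHg rise at an assumed share of 5 to 20% with full reversal. The documents give neither the number of retained dropouts with ABPM nor any evidence on reversal.

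A confidence interval would not settle whether a rise of 3 to 5 mmHg exists, given an assumed half-width of 4.3 to 6.4 mmHg. Its value is to show how little two similar means would exclude. Every mmHg figure here is an assumption range, since the plan gives no ABPM numbers or SD. The change is worth making, but the trial's main conclusions do not depend on it.

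**What to change.** 1. Reconcile the age range across the protocol synopsis, Protocol Table 3, SAP 1.4.3 and SAP 4.5.15.
2. In SAP 4.5.15, summarise patients aged 12 and over as the endpoint population and show those under 12 separately.
3. For change in 24-hour SBP, DBP and heart rate at Week 24 and EOT, report the baseline-adjusted setmelanotide minus placebo difference with 95% CI, descriptively and without a formal test.
4. State how off-drug recordings are handled. Keep the all-recordings table as the main one and place an on-drug table beside it, labelled as a subset selected after randomisation. The e-diary dosing log in Protocol 5.5.4 already holds the dosing information.
5. State in SAP 4.3.6.11 whether blood pressure there includes ABPM.

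The cost is SAP wording, an aligned synopsis and a few extra tables. No new data are needed. The drawback is a wide interval, which the report should present as such.

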## 5. CHANGES TO PLANNED ANALYSES

CCI

CCI

